9.4.3.2. Categorical Efficacy Analyses

The proportion of participants in each treatment group meeting prespecified binary efficacy outcomes will be estimated for each postbaseline visit. The estimates will be provided from a longitudinal Bayesian model that includes all postbaseline observations. The average weekly score for the NRS will be computed and used in the comparison between treatment groups within an ISA.

The prespecified binary efficacy outcomes include the proportion of participants

- with a pain reduction greater than or equal to 30%, 50%, and 70% from baseline as measured by the NRS average pain scale
- with a pain reduction greater than or equal to 30%, 50%, and 70% from baseline as measured by the NRS worst pain scale
- with a pain reduction greater than or equal to 30%, 50%, and 70% from baseline as measured by the VAS
- with at least 2-point reduction from baseline on the NRS average pain scale
- with at least 2-point reduction from baseline on the NRS worst pain scale, and
- with an improvement in physical function greater than or equal to 30%, 50%, and 70% from baseline as measured by the physical functioning scales defined in the DSA.

The models will include treatment, time interval (or visit), interaction between treatment by time interval (or visit), average baseline pain severity category (moderate vs severe) as defined by baseline NRS less than 7 versus baseline NRS greater than or equal to 7 and pooled investigative site, unless otherwise noted in the ISA SAP. The ISA SAP will contain the exact specification of the model and parameters for the respective ISA.

9.4.3.3. Time to Event Efficacy Analyses

A Kaplan-Meier analysis will be conducted for these outcomes:

- time to first pain reduction of at least 30%, 50%, and 70% from baseline as measured by the NRS average pain scale
- time to first pain reduction of at least 30%, 50%, and 70% from baseline as measured by the NRS worst pain scale
- time to first pain reduction of at least 2-points from baseline on the NRS average pain scale, and
- time to first pain reduction of at least 2-points from baseline on the NRS worst pain scale.

For the time to event analyses, participants who do not have the event of interest by the end of the treatment phase will be treated as a right censored observation.

For these analyses, the average score over a weekly interval for the NRS will be computed and used in the analysis. In addition, time to event analyses will also be performed using the daily NRS scores.

The ISA SAP will contain the exact specification of the model and parameters for the respective ISA.

9.4.4. Tertiary/Exploratory Endpoints

A cumulative distribution function of percent change from baseline to endpoint for the NRS average and worst pain scales and the VAS will be provided for each treatment group. No statistical comparisons will be made between the groups.

Appropriate statistical methods will be used to understand the relationship of the biomarker endpoints to other clinical endpoints in terms of treatment effect. Any intervention-specific tertiary/exploratory analyses will be described in the respective ISA.

9.4.5. Treatment Group Comparability

9.4.5.1. Participant Disposition

Participants who discontinue from the study will be identified, and the extent of their participation in the study will be reported for each ISA. A detailed description of participant disposition and the reasons for discontinuation will be summarized by treatment group for each ISA at the end of the study. Intervention-specific analyses will be detailed in each respective ISA.

9.4.5.2. Participant Characteristics

Participant characteristics and baseline clinical measures will be summarized for each treatment period. For all participant characteristics, the summaries will include descriptive statistics for continuous measures (sample size, mean, SD, median, minimum, and maximum) and for categorical measures (sample size, counts and percentages).

Additional intervention-specific analyses will be specified in each respective ISA.

9.4.5.3. Concomitant Therapy

Concomitant medications used during the study will be listed and summarized for each ISA.

The average intake (in milligrams) per day of the approved pain rescue therapy acetaminophen will be summarized by weekly intervals for each treatment group. The average intake per day over the entire placebo-controlled phase will also be compared and summarized between treatment groups.

9.4.5.4. Treatment Compliance

Treatment compliance with the study intervention will be summarized by treatment for each ISA. Intervention-specific analyses will be described in the respective ISAs.

9.4.6. Safety Analyses

All safety analyses will be conducted on the Safety Population for each ISA.

9.4.6.1. Vital Signs Analyses

The mean change from baseline in pulse rate, systolic and diastolic blood pressure, temperature, and weight will be summarized for each treatment group. The incidence of treatment-emergent abnormal high and low vital signs and weight will be summarized by treatment group.

9.4.6.2. Electrocardiogram Analyses

The mean change from baseline will be summarized by treatment group for the following ECG parameters: heart rate, PR interval, QRS duration, QT interval, and QTcF interval. All analyses of corrected QT will be carried out using Fridericia's correction factor [$QTcF=QT/RR^{0.333}$]). The incidence of treatment-emergent abnormal high and low changes in heart rate, PR interval, QRS duration, and QTcF interval will be summarized.

The number and percentage of participants with a QT interval greater than 500 msec and the percentage with a QTcF greater than 500 msec will be summarized for each treatment group. The percentage of participants who experienced a treatment-emergent increase from the maximum baseline in QTcF interval of greater than 30 msec, 60 msec, or 75 msec at any time will also be summarized.

9.4.6.3. Laboratory Assessment Analyses

The mean change from baseline laboratory assessments will be summarized for each treatment group. The incidence of treatment-emergent abnormal high and low laboratory assessments will be summarized by treatment group. In addition, listings of abnormal findings for laboratory analyte measurements, including qualitative measures, will be provided.

9.4.6.4. Adverse Events

Adverse events will be classified by system organ class and preferred term as defined by the Medical Dictionary for Regulatory Activities (MedDRA). A treatment-emergent adverse event (TEAE) is defined as an event that first occurs or worsens in severity after baseline and on or before the date of the last visit within the dosing period.

All conditions existing prior to randomization at Visit 3 will be used as baseline. The postbaseline visits during the placebo-controlled phase will be included as the postbaseline period for analysis.

For events that are gender specific, the denominator and computation of the percentage will only include participants of the given gender.

All AEs will be summarized by

- number and percentage of participants who experience TEAEs
- TEAEs by maximum severity
- TEAEs related to study intervention
- follow-up emergent AEs
- AEs leading to discontinuation of intervention
- AEs leading to discontinuation from the study
- SAEs, and
- deaths.

All AEs, including preexisting conditions, will be listed by

- participant
- visit
- preferred term

- treatment group
- severity (mild, moderate, or severe), and
- possible relationship to the study intervention.

Adverse events of special interest will be defined in the ISA.

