
The appropriate time to schedule Visit 2 depends on the 5-half-life washout period required for medications taken for chronic pain and the minimum 7-day preliminary data entry period (PDEP) required prior to Visit 3.

The washout period should begin at Visit 2.

If participants are not taking medication for chronic pain during screening, a washout is not required.

The recommended minimum washout duration is 2 days. If a participant is taking a medication that requires a tapered discontinuation that is longer than 5 half-lives, then the medication label instructions for discontinuation should be followed.

The 7-day PDEP is required for all participants regardless of washout duration. The PDEP includes daily participant reporting of pain severity on the numeric rating scale and information on rescue medication use.

The screening period is complete upon investigator confirmation of all screening procedures for the master and all active ISAs.

Visit 3

The appropriate time to schedule Visit 3 is after completion of the washout period and required PDEP. Visit 3 is the common point of randomization within the master protocol for each ISA.

Follow-Up Visit

Visits beyond the 8-week treatment period may be specified in an individual ISA.

Randomization and Blinding

All participants will be centrally randomized to an ISA and to study intervention within an ISA using an IWRS. The IWRS will be programmed with unblinding instructions. In case of an emergency, the investigator has the sole responsibility for determining if unblinding of a participants' intervention assignment is warranted. However, the investigator should make all attempts to contact the Medical Monitor in advance of unblinding.

Participants

Male and female participants are eligible for inclusion in the study if they have a history of daily pain based on participants' report or medical history.

Disclosure Statement:

This is a master protocol for randomized, investigator- and participant-blind, placebo-controlled, Phase 2 clinical trials of multiple interventions for the treatment of chronic pain.

Number of Participants:

The number of participants will be specified in each respective ISA.

Intervention Groups and Duration:

Information about study intervention is provided in each respective ISA.

Each ISA will have an 8-week double-blind treatment period.

[figure not shown]

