1.3. Schedule of Activities (SoA)

The activities applicable to all disease states and interventions studied under the master protocol are described in the SoA below.

	Screening ^a		Double-Blind Treatment Period						
H0P-MC-CPMP Master Protocol	Screening Visit for Master	Pre-Randomization Screening Visit	Randomization to ISA					Early Discontinuation	Notes
Visit Number	V1 ^b	V2 ^c	V3	V4	V5	V6	V7	ED	Visits after V7 may be specified in the ISA.
Study Week	Up to -6 months	-10 to -7 days for most participants	0	2	4	6	8		
Procedure/ Assessments									
Informed consent for master protocol	X								
Informed consent for ISA	X								ISA-specific informed consent may occur after other V1 procedures and prior to beginning the medication washout if the ISA is not available at the time of initial screening.
Evaluate master protocol I/E criteria	X	X	X						
Pain medication washout		X							Duration of washout is at least 5 half-lives of the longest half-life medication taken for pain. Recommended minimum washout duration is 2 days. If participants are not taking medication for chronic pain during screening, a washout is not required.
PDEP		X							7-day minimum NRS data and rescue use medication collected daily at home post washout and prior to randomization.
Medical history	X								
Family history	X								

	Screening ^a		Double-Blind Treatment Period						
H0P-MC-CPMP Master Protocol	Screening Visit for Master	Pre-Randomization Screening Visit	Randomization to ISA					Early Discontinuation	Notes
Visit Number	V1 ^b	V2 ^c	V3	V4	V5	V6	V7	ED	Visits after V7 may be specified in the ISA.
Study Week	Up to -6 months	-10 to -7 days for most participants	0	2	4	6	8		
Demographics	X								Including age, gender, race, and ethnicity
Physical examination	X	X ^d							
Weight	X	X ^d	X	X	X	X	X	X	
Height	X								
Vital signs	X	X ^d							Pulse rate, respiratory rate, blood pressure, and temperature taken with participant in a sitting position.
ECG	X	X ^d	X					X	Triplicate ECGs. Post randomization ECGs are included in each ISA.
AEs		X	X	X	X	X	X	X	Any events that occur after signing the ICF are considered AEs as defined in Section 10.3.
Preexisting conditions	X								Preexisting conditions not identified at V1 and started prior to signing the ICF should be recorded.
Concomitant medications	X	X	X	X	X	X	X	X	
Scales, Questionnaires, and Outcome Measures									
VAS for pain	X	X	X	X	X	X	X	X	V2 procedure should be repeated if >60 days from V1

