7.1. Discontinuation of Study Intervention

In rare instances, it may be necessary for a participant to permanently discontinue (definitive discontinuation) study intervention.

If study intervention is definitively discontinued, the study participant will not remain in the master protocol or ISA. See the master protocol and ISA SoA for data to be collected at the time of discontinuation of study intervention and follow-up and for any further evaluations that need to be completed.

Additional criteria for discontinuation may be included in each ISA. If an ISA criterion is more restrictive, it should be applied for those participants in the respective ISA.

Participants **may** be discontinued from study intervention if these situations occur:

- based on a specific AE profile, as recommended by the Assessment Committee (AC), the Medical Monitor, or the study sponsor physician/scientist, in discussions with the Principal Investigator
- incorrect enrollment
- severe noncompliance to the study protocol in the judgment of the investigator
- participants answered 'yes' to Question 4 or 5 on the 'Suicidal Ideation' portion of the C-SSRS, or
- participants answered 'yes' to any of the suicide-related behaviors on the Suicidal Behavior portion of the C-SSRS.
 - a psychiatrist or appropriately trained professional may assist in the decision to discontinue the participant for C-SSRS responses.

Liver Safety

Discontinuation of the intervention should be considered when a participant meets one of the following conditions after consultation with the sponsor-designated Medical Monitor.

- ALT or AST $>8 \times$ ULN
- ALT or AST $>5 \times$ ULN for more than 2 weeks
- ALT or AST $>3 \times$ ULN and either TBL $>2 \times$ ULN or international normalized ratio (INR) >1.5 , or
- ALT or AST $>3 \times$ ULN with the appearance of fatigue, nausea, vomiting, right upper quadrant pain or tenderness, fever, rash, and/or eosinophilia ($>5\%$).

The discontinuation criteria are applicable for participants with no known liver disease and normal or near normal baseline liver tests of

- $ALT < 2 \times ULN$
- $TBL < 1.5 \times ULN$, and
- $ALP < 1.5 \times ULN$.

Cardiovascular Safety

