7.2. Participant Discontinuation/Withdrawal from the Study

A participant may withdraw from the master protocol or ISA:

- at any time at his/her own request
- at the request of his/her designee (for example, parents or legal guardian)
- at the discretion of the investigator for safety, behavioral, compliance, or administrative reasons
- if the participant becomes pregnant
- if enrollment in any other clinical study involving an investigational intervention or enrollment in any other type of medical research judged not to be scientifically or medically compatible with the master protocol or ISA, or
- if the participant, for any reason, requires treatment with another therapeutic agent that has been demonstrated to be effective for treatment of the study indication, discontinuation should occur prior to introduction of the new agent.

Discontinuation is expected to be uncommon.

If possible, an early discontinuation visit should be conducted at the time of discontinuing from the master protocol/DSA or an ISA. Data to be collected at the time of study discontinuation and follow-up and for any further evaluations that need to be completed will be included in the master protocol/DSA and ISA. The participant will be permanently discontinued both from the study intervention and from the master protocol/DSA or ISA at that time.

If the participant withdraws consent for disclosure of future information, the sponsor may retain and continue to use any data collected before such a withdrawal of consent. If a participant withdraws from the study, he/she may request destruction of any samples taken and not tested, and the investigator must document this in the site study records.

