7.3. Lost to Follow-Up

A participant will be considered lost to follow-up if he or she repeatedly fails to return for scheduled visits and is unable to be contacted by the study site. Study personnel or designee are expected to make diligent attempts to contact participants who fail to return for a scheduled visit or were otherwise unable to be followed up by the site.

Information about the discontinuation of specific sites or of the study are handled as part of the regulatory, ethical, and trial oversight considerations in Appendix 1.

8. Study Assessments and Procedures

Master protocol procedures and their timing are summarized in the SoA (Section 1.3). Additional SoAs are included in the DSA and may also be included in each ISA.

Protocol waivers or exemptions are not allowed.

Immediate safety concerns should be discussed with the sponsor immediately upon occurrence or awareness to determine if the participant should continue or discontinue study intervention.

Adherence to the study design requirements, including those specified in the SoA, is essential and required for study conduct.

All screening evaluations must be completed and reviewed to confirm that potential participants meet all eligibility criteria for the master protocol, DSA, and each active ISA. The investigator will maintain a screening log to record details of all participants screened and to confirm eligibility or record reasons for screening failure, as applicable.

Self-reported questionnaires will be administered by either an electronic device or on paper. Participants' self-assessments should be completed before any clinical examinations are performed.

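### The TEAE window closes at a visit rather than at the last dose, so an early stopper without an early discontinuation visit can have on-drug events left out of the TEAE tables

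*Protocol*

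**What the plan says.** Section 9.4.6.4 defines a treatment-emergent adverse event (TEAE) as one that "first occurs or worsens in severity after baseline and on or before the date of the last visit within the dosing period". Baseline is the set of conditions present before randomization at Visit 3. The next paragraph adds a second, phase-based boundary: "The postbaseline visits during the placebo-controlled phase will be included as the postbaseline period for analysis". Neither sentence mentions the last dose or the ED visit, and the protocol nowhere defines the dosing period.

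Other provisions that bear on the rule:

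- **Treatment length and visits.** The synopsis (Section 1.1) states: "Each ISA will have an 8-week double-blind treatment period". The schedule of activities (Section 1.3) puts Visits 3 to 7 at weeks 0, 2, 4, 6 and 8. It also has an ED column, in which adverse events are marked for collection.
- **Stopping drug.** Section 7.1: "If study intervention is definitively discontinued, the study participant will not remain in the master protocol or ISA".
- **ED visit.** Section 7.2: "If possible, an early discontinuation visit should be conducted at the time of discontinuing from the master protocol/DSA or an ISA".
- **Loss to follow-up.** Section 7.3 recognises the participant who "repeatedly fails to return for scheduled visits and is unable to be contacted by the study site".
- **Collection of events.** Section 8.3 allows a caregiver or representative to report an event, and Section 8.3.1 continues collection until participation ends.
- **Other summaries.** Section 9.4.6.4 also tabulates "AEs leading to discontinuation of intervention", events leading to study discontinuation, SAEs, deaths and follow-up emergent events. The last term is not defined.

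**The concern.** An exposure-based window asks whether an event arose while the participant was on drug. This rule asks whether it arose by a certain visit. For someone who reaches Visit 7 the two questions give nearly the same answer. For someone who stops between visits and is not seen again, they can differ. Such a participant leaves the study, so no later scheduled visit moves the cut-off forward.

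The event can still reach the database through a caregiver or a telephone contact. By the stated rule it would then be absent from three summaries that depend on the TEAE flag: incidence, maximum severity and relatedness. It could sit under SAEs, deaths or discontinuations and be missing from the TEAE tables of the same report, or be labelled follow-up emergent although it occurred on drug. If stops for poor tolerability are more frequent on active treatment, the omission is unequal between arms and makes active treatment look slightly better tolerated.

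The rule is common to every ISA, and Section 4.1 expects interventions to enter for 5 to 7 years, so the gap would be repeated.

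**Working it through.** The protocol gives no adverse event rate, discontinuation rate or sample size for this rule, so there is no planned figure to reproduce. The check has two parts.

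**1. Which visits close the window?**

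| Participant | Last visit in the window | On-drug event before stopping |
|---|---|---|
| Completes to Visit 7 | Visit 7 | TEAE |
| Stops early, ED visit held | ED visit, on the natural reading | TEAE |
| Stops early, no ED visit | Previous scheduled visit | Not a TEAE if after that visit |

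The second row rests on two facts. The schedule places the ED column in the double-blind treatment block, and Section 7.2 times the visit at discontinuation. The wording of Section 9.4.6.4 does not confirm it.

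**2. How much on-drug time can fall outside?** Inputs from the schedule of activities are nominal visit days 0, 14, 28, 42 and 56. Assumptions of this review are dosing on every day up to the last dose, every earlier visit attended on its nominal day, and a last-dose day d uniform over days 1 to 55.

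Uncounted days for a stopper without an ED visit: g(d) = d − (latest visit day not after d).

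- Example: an event on day 25, with stopping on day 25 and no ED visit, has day 14 as its last visit. The event lies 25 − 14 = 11 days past the cut-off.
- Someone who stops on days 1 to 13 has only Visit 3 (day 0) as last visit, so no on-drug event after that day can qualify.
- Range of g: 0 to 13 days.
- Sum of g: in each of the four intervals between visits the days add to 0 + 1 + … + 13 = 91, so the total is 4 × 91 = 364. The mean is 364 / 55 = 6.6 days.
- The sum of d from 1 to 55 is 1,540, so the share of these participants' on-drug time is 364 / 1,540 = 24%.

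Let q be the proportion of an arm that stops early and f the proportion of those without an ED visit. The mean last-dose day of early stoppers is 1,540 / 55 = 28, and completers contribute 56 days.

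Share of the arm's on-drug time outside the window = q × f × 6.618 / (28q + 56(1 − q)).

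| q (assumed) | f = 0 | f = 0.1 | f = 0.5 | f = 1 |
|---|---|---|---|---|
| 5% | 0 | 0.06% | 0.30% | 0.61% |
| 10% | 0 | 0.12% | 0.62% | 1.24% |
| 20% | 0 | 0.26% | 1.31% | 2.63% |
| 30% | 0 | 0.42% | 2.09% | 4.17% |

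For example, q = 10% and f = 1 give 0.1 × 6.618 / (2.8 + 50.4) = 0.6618 / 53.2 = 1.24%.

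These are shares of time, not of events. Events may cluster near the moment of stopping, so the share of events could be higher. In the other direction, a participant with an earlier TEAE is already counted in overall incidence. The document gives nothing with which to quantify either effect.

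**The case against.** The case for leaving the text alone is substantial.

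- **The ED visit covers most early stoppers.** It is planned at discontinuation, it collects adverse events, and it sits in the double-blind block. This stands, and it limits the point to participants without that visit. A reader might go further and infer that an ED visit after the last dose is outside the dosing period, so that even those who attend are undercounted. The protocol does not support this. Applied evenly, the same strict reading could exclude Visit 7 whenever it follows the last dose, and the sentence on postbaseline visits points to a phase-based period.
- **Serious or treatment-limiting events remain visible.** The separate summaries and the listing of all adverse events keep them in the report by treatment group. This stands for visibility. It does not correct TEAE incidence, severity or relatedness.
- **The numbers affected may be very small.** Section 7.2 expects discontinuation to be uncommon, and for a participant who cannot be contacted the event may never be learned of at all. Both points stand. A reader might still infer that the omitted events are often those that caused stopping, or that an excess on active treatment could vanish from the tables. No rate in the protocol supports either inference.
- **Regimens are not visible here.** Dosing is set in the ISAs, so daily exposure up to day 55 is an assumption. A visit-based rule is a workable common denominator across unknown regimens. This argues for keeping the visit as one limb of the rule, not as the only one.
- **The SAP may settle it.** A SAP could add detail, but the protocol already states the cut-off, so this is not merely detail left for later.

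**Conclusion.** The point holds in a narrow form. As written, the rule omits on-drug events that follow the last visit in participants who stop between visits and have no ED visit. It also leaves unstated whether the ED visit counts. For each such participant the uncounted time is 0 to 13 days, 6.6 days on average, given nominal visit days, no missed visits, daily dosing and stops spread evenly; a missed visit would lengthen it. Under the assumed ranges above this is between 0 and about 4% of an arm's on-drug time, and at most 1.24% when 10% stop early.

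The effect on TEAE incidence cannot be calculated from the document. Its direction would favour active treatment only if early stops without an ED visit, accompanied by on-drug events, are more common there. That is plausible but not shown. The start of the window, after baseline at Visit 3, is not at issue and nothing here calls for changing it.

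This is a small but real flaw in a stated definition. It is worth correcting because the definition serves every ISA and the correction is cheap.

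**What to change.** In Section 9.4.6.4 and the master protocol SAP, keep the present start of the window and end it at the later of:

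- (a) the last visit of the placebo-controlled phase, with the ED visit named as part of that phase; and
- (b) the date of the last dose of study intervention, with any further interval left to the ISA.

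Drop or define the term dosing period so that it agrees with the sentence on postbaseline visits. Define follow-up emergent events as those that first occur or worsen after this window.

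State a rule for estimating the last-dose date when it is not verified. Section 6.4 records dates and times of supervised doses, but home dosing is checked at visits by questioning and by counting returned supplies. A home-dosing participant without an ED visit is therefore the one most likely to need an estimate.

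The cost is a change of wording in one definition and one imputation rule, with no new visits. TEAE rates may rise slightly, and some events will be classified on an estimated date.
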